### 11.2 Determination of sample size

Considering the primary endpoint of the study as the reduction from baseline to week 8 in LDL cholesterol level and the data available from literature [Phytomedicine. 2016 Oct 15; 23(11):1113-8], a reduction of LDL level of approximately 10% is expected after the intake of the nutraceutical. Therefore, a mean difference of 15 mg/dL in the reduction of LDL cholesterol level at week 8 between the nutraceutical treatment group and the placebo group is considered clinically significant.

Assuming a baseline LDL level of  $145 \pm 19$  mg/dL, a power of 90% and a 5% two-sided alpha level to detect a difference in mean change in LDL from baseline to week 8 equal to 15 mg/dL between the nutraceutical and the placebo group, the total number of patients to be evaluated should be 35 per treatment arm in a 1:1 ratio (NQuery Advisor, 7.0). Allowing for an approximate 20% dropout rate, at least 88 patients should be randomized: 44 patients in each treatment group.

### 11.3 Analysis populations

Patients without a valid or adequately obtained Informed Consent Form (ICF) will be excluded from any analysis population.

The following analysis populations will be defined for statistical analyses:

- **Full Analysis Set (FAS):** All patients to whom study treatment has been assigned by randomization and who have the assessment for LDL cholesterol at visit 4 (week 8). According to the intent-to-treat principle, patients will be analyzed according to the treatment they have been assigned to during the randomization procedure. The primary and secondary analysis will be based on the FAS.
- **Per Protocol (PP) Set:** All patients in the FAS who have no major protocol deviations. All major protocol deviations leading to exclusion from the PP set will be detailed in the analysis plan. Results of the analysis of the primary variable conducted in the PP set will be considered as supportive.

## Menarini Group

Sponsor: A. Menarini Industrie Farmaceutiche Riunite S.r.l.

Amended Protocol Version 4.0 of 16.04.2018

Study Code: MEIF/16/MOF-Col/001

- **Tolerability Set:** All patients who received at least one dose of investigational product. Patients will be analyzed according to the treatment actually received (if different from treatment assigned through randomization).

### 11.4 Analysis variables

- The primary variable of the study is the change from baseline to Week 8 in LDL cholesterol levels
- The secondary variables of the study are defined as change from baseline to Week 8 in:
  - Total blood cholesterol
  - Blood HDL-cholesterol
  - Blood non-HDL cholesterol
  - Blood triglycerides
  - Apolipoprotein B
  - TC/HDL and LDL-C/HDL risk ratios
  - Pulse Volume (PV) waveform (endothelial reactivity)
  - Glycemia, ALT, AST, gamma-GT, creatinine, uric acid, CPK
- Other variables are as follows:
  - Change from baseline at each assessment time point for each laboratory parameter
  - Adverse Events
  - Vital Signs
  - Weight
  - Height
  - Waist Circumference
  - Index of Central Obesity (ICO)
  - Body Mass Index (BMI)
  - Hepatic Steatosis Index (HSI)
  - Lipid Accumulation Product (LAP)

### 11.5 Statistical analysis

#### Patient demographics and other baseline characteristics

All data about patient demographics and baseline characteristics will be summarized in the FAS, overall and by treatment group, by means of summary descriptive statistics.

The number and percentages of subjects meeting all eligibility criteria at screening will be provided. The analysis populations will be described and the reasons for excluding a patient

## Menarini Group

Sponsor: A. Menarini Industrie Farmaceutiche Riunite S.r.l.

Amended Protocol Version 4.0 of 16.04.2018

Study Code: MEIF/16/MOF-Col/001

from any particular population will be provided with the number of protocol deviators per each criterion.

A complete description of patients' disposition will be provided, overall and by treatment group specifying the number of randomized patients, the number of patients at each visit, the number of completed and discontinued patients and the reason for the discontinuation.

Medical history data will be presented by MedDRA dictionary system organ class and preferred term, overall and by treatment group.

### **Treatments (study treatment, concomitant therapies, compliance)**

The Tolerability set will be used for the analyses on treatment administration, compliance, concomitant medications and adverse events.

Extent of exposure is defined as the difference in days between the date of last treatment administration and the date of first treatment administration plus one, regardless of unplanned intermittent discontinuations.

Overall treatment compliance is defined as the actual number of capsules taken compared to the planned treatment duration (i.e. extent of exposure).

Extent of exposure and treatment compliance will be summarized by means of descriptive statistics, overall and by treatment group. The percentage of patients per compliance level will be also summarized:

- $\leq 80\%$
- $>80\%$  and  $\leq 120\%$
- $>120\%$

A subject that has taken at least 80% and no more than 120% of the required treatment will be considered compliant.

Dose reductions and dose interruptions (including the reasons) will be listed and summarized overall and by treatment group.

Concomitant medications and significant non-drug therapies prior to and after the start of the study treatment will be presented by WHO Drug Dictionary ATC class and preferred term, overall and by treatment group.

### **Primary variable**

The statistical analysis of the primary variable will be performed on the FAS population and on the PP population as supportive.

No alpha level adjustment for multiplicity will be adopted.

All data available will be used for analysis and no technique for missing data imputation will be adopted.

## Menarini Group

Sponsor: A. Menarini Industrie Farmaceutiche Riunite S.r.l.

Amended Protocol Version 4.0 of 16.04.2018

Study Code: MEIF/16/MOF-Col/001

Summary statistics of raw data and change from baseline at each assessment time point for LDL cholesterol levels will be presented overall and by treatment group.

An analysis of covariance (ANCOVA) model will be estimated on the changes from baseline to Week 8 in LDL cholesterol levels considering treatment group as factor and baseline value of LDL cholesterol as continuous covariate. Results will be reported as Least-Square Means together with associated two-tailed 95% CI and p-value. If the assumption of normality of residuals is violated, the ANCOVA model will be fitted on rank transformed data.

### **Secondary variables**

The statistical analyses of the secondary variables will be performed on the FAS population. Given the exploratory nature of the secondary objectives of the study, no alpha level adjustment for multiplicity will be adopted.

The prevalence approach will be applied, and therefore no technique for missing data imputation will be adopted.

The same statistical models described for the analysis of the primary variable will be applied.

### **Other variables**

All the other analyses will be performed on the Tolerability set.

No missing data handling approach will be applied.

### **Adverse Events**

The incidence of Adverse Events (AEs) and Serious Adverse Events (SAEs) recorded throughout the study will be presented.

According to the onset date of the event, AEs will be defined as follows:

- treatment-emergent AE, those events with an onset date after treatment initiation
- non-treatment-emergent AE, those events with an onset date between informed consent and treatment initiation

Non treatment-emergent AEs will be listed only.

Treatment-emergent AEs will be summarized by MedDRA dictionary system organ class and preferred term. A summary of treatment-emergent AEs by preferred term and severity will be also provided. For analysis purposes, all treatment-emergent AEs defined as “certain”, “probable”, “possible” or “unassessable” will be considered as product related. If the relationship to study treatment is missing, the treatment-emergent AE will be considered treatment-related. All related treatment-emergent AEs, treatment-emergent AEs with an outcome of death, treatment-emergent AEs leading to discontinuation of treatment will be summarized by MedDRA dictionary system organ class and preferred term and will also be listed. Serious treatment-emergent AEs will be summarized similarly. Percentages will be based on the number of subjects in the Tolerability set.

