## Menarini Group

Sponsor: A. Menarini Industrie Farmaceutiche Riunite S.r.l.

Amended Protocol Version 4.0 of 16.04.2018

Study Code: MEIF/16/MOF-Col/001

Once inclusion/exclusion criteria are confirmed, eligible patients will be asked to return no later than 3 days after Visit 2 for randomization and treatment dispensation. The day of randomization will be considered as Day 0.

Weight, waist circumference, Index of Central Obesity (ICO), Body Mass Index (BMI), Hepatic Steatosis Index (HSI), Lipid Accumulation Product (LAP)
Heart rate, blood pressure (average of three measurements)
Hematology/clinical chemistry in fasting condition (total cholesterol, LDL-cholesterol, HDL and non-HDL cholesterol, triglycerides, risk ratio, B apolipoproteins, LDL-C/Apo B, glycemia, ALT, AST, gamma-GT, CPK, uric acid, creatinine, eGFR with MDRD formula)
Endothelial reactivity test (Endocheck®)
Urine Pregnancy Test (dipstick)
Diet evaluation (see Appendix 1)
Dispensation of treatment
Concomitant medication
Adverse events

Eligible patients will be randomly assigned to one of the two groups in a 1:1 ratio (45 subjects per group) and treated with phytosterols 800 mg + DIF1STAT® or placebo, one tablet a day for 8 weeks.

**Visit 3 (Day 28)** (intermediate) will take place  $28 \pm 3$  days after Day 0.

During V3, the following evaluations are performed:

Weight, waist circumference, Index of Central Obesity (ICO), Body Mass Index (BMI), Hepatic Steatosis Index (HSI), Lipid Accumulation Product (LAP)
Heart rate, blood pressure (average of three measurements)
Hematology/clinical chemistry in fasting condition (total cholesterol, LDL-cholesterol, HDL and non-HDL cholesterol, triglycerides, risk ratio, B apolipoproteins, LDL-C/Apo B, glycemia, ALT, AST, gamma-GT, CPK, uric acid, creatinine, eGFR with MDRD formula)
Diet evaluation (see Appendix 1)
Concomitant medication
Accountability and compliance with treatment
Treatment tolerability evaluation (adverse events, if any)

**Visit 4 (Day 56)** (end of study) will take place  $28 \pm 3$  days after V3.

During the last visit the following evaluations are performed:

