## 10. ASSESSMENT OF SAFETY

### 10.1 Adverse events (AE)

An adverse event (AE) is any untoward medical occurrence in a patient administered the product and which does not necessarily have to have a causal relationship with the product.

Adverse events should be recorded in the Adverse Events CRF under the signs, symptoms or diagnosis associated with them accompanied by the following information.

- severity grade
  - mild: usually transient in nature and generally not interfering with normal activities
  - moderate: sufficiently discomforting to interfere with normal activities
  - severe: prevents normal activities
- Relationship to the investigational product (no/yes)
- Duration (start and end dates) or if the event is ongoing an outcome of not recovered/not resolved should be reported.
- Action taken regarding investigational treatment
- Whether other medication or therapies have been taken
- Outcome (not recovered/not resolved; recovered/resolved; recovering/resolving, recovered/resolved with sequelae; fatal; or unknown)
- Whether it constitutes a serious adverse event (SAE)

A **serious adverse event** (SAE) is any untoward medical occurrence that at any dose:

- Results in death, or
- Is life-threatening, or
- Requires inpatient hospitalization or prolongation of existing hospitalization, or
- Results in persistent or significant disability/incapacity, or

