1. INTRODUCTION

1.1. CHANGES FROM THE STUDY PROTOCOL

Not applicable.

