6.6.1. Adverse Events

According to the onset date of the event, AEs will be defined as follows:

- treatment-emergent AE, those events with an onset date after treatment initiation
- non-treatment-emergent AE, those events with an onset date between informed consent and treatment initiation

The incidence of Adverse Events (AEs) and Serious Adverse Events (SAEs) recorded throughout the study will be presented by actual treatment. Non treatment-emergent AEs will be listed separately.

Tables reporting a general summary of AEs will be produced specifying the number of total events and the absolute and relative frequency of subjects with AEs. As a patient may have more than one AE, the total number of AEs could be greater than the total number of patients. Absolute and relative frequency of patients with drug-related AEs, severe AEs, SAEs, AEs with an outcome of death, AEs leading to temporary or permanent discontinuation of treatment will be also reported. Product-related AEs will be the AEs with causality equal to “certain”, “probable”, “possible” or “unassessable”; if the relationship to study treatment is missing, the treatment-emergent AE will be considered drug related as well. AEs leading to temporary or permanent discontinuation of treatment will be the AEs with action taken with investigational product equal to “Drug interrupted” or “Drug withdrawn.”

Statistical Analysis Plan

Sponsor: A. Menarini Industrie Farmaceutiche Riunite S.r.l.

Protocol number: MEIF/16/MOF-Col/001

Treatment-emergent AEs will be summarized by MedDRA dictionary System Organ Class (SOC) and Preferred Term. A summary of treatment-emergent AEs by preferred term and severity will be also provided.

All related treatment-emergent AEs, treatment-emergent AEs with an outcome of death, treatment-emergent AEs leading to discontinuation of treatment will be summarized by MedDRA dictionary System Organ Class (SOC) and Preferred Term (PT) and will also be listed.

Serious treatment-emergent AEs will be summarized similarly.

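### Protocol 10.1 records AE relationship as no/yes, but the related-AE rule in Protocol 11.5 and SAP 6.6.1 uses graded causality terms, with no mapping between them (minor)

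*Protocol*

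**What the plan says.** Collection is described in Protocol 10.1: "Adverse events should be recorded in the Adverse Events CRF under the signs, symptoms or diagnosis associated with them accompanied by the following information". One item in the list that follows is "Relationship to the investigational product (no/yes"). The same list spells out the response options for severity and for outcome, so the two values read as the options for this item as well.

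Analysis is described in Protocol 11.5, Adverse Events: "all treatment-emergent AEs defined as “certain”, “probable”, “possible” or “unassessable” will be considered as product related". The next sentence deals with blanks: "If the relationship to study treatment is missing, the treatment-emergent AE will be considered treatment-related".

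SAP 6.6.1 carries the rule over as a definition: "Product-related AEs will be the AEs with causality equal to “certain”, “probable”, “possible” or “unassessable", again with missing counted as related. Among its planned outputs is "Absolute and relative frequency of patients with drug-related AEs". It also plans a table of related treatment-emergent AEs by system organ class and preferred term, and a listing of them.

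**The concern.** The analysis rule is written for values that the collection section does not provide. A 'yes' is the clearest statement an investigator can make under Protocol 10.1 that an event is related, yet it does not appear in the rule that decides which events are reported as related. Counting blanks and unassessable events as related shows that the rule was meant to be cautious. Applied as written to a no/yes field, it does the reverse: it counts the blanks and passes over the events that the investigator attributed to the product.

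At stake are the outputs that describe tolerability attributed to the product. A pre-specified plan should not leave their content to whoever programs the flag.

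**Working it through.** No sample size, power or rate is involved, and the plan states no figure to reproduce. The check sets the texts side by side and applies the rule to each value that the field could hold.

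**Step 1: if the field is no/yes, as Protocol 10.1 describes.**

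| Value recorded | Protocol 11.5 | SAP 6.6.1, read literally |
|---|---|---|
| yes | not mentioned | not one of the four values, so not related |
| no | not mentioned | not one of the four values, so not related |
| missing | related | related |

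The related set then consists of the missing values alone. The two documents differ slightly in form. Protocol 11.5 says that events in the four categories count as related, without saying that no others do. SAP 6.6.1 is restrictive: it says what the product-related events are. The literal exclusion of 'yes' therefore comes from the SAP wording; the Protocol wording leaves 'yes' undefined.

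**Step 2: if the field is graded, as Protocol 11.5 and SAP 6.6.1 presuppose.**

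Every value has a defined place. The four named categories and missing are related, and any other grade is not. The rule works, and the only faulty text is the no/yes entry in Protocol 10.1.

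**Step 3: look for a bridge.**

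No section of either document maps 'yes' or 'no' to the graded terms, and none sets up a graded causality scale for data collection. So at least one of the texts must be wrong; which one depends on the CRF.

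**Step 4: list what uses the flag.**

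- Uses it: the frequency of patients with drug-related AEs, the related-AE table by system organ class and preferred term, and the related-AE listing.
- Does not use it: the tables of all treatment-emergent AEs, the serious, fatal and discontinuation AE outputs, the laboratory summaries including CPK and the liver enzymes, and the primary and secondary efficacy analyses.

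**The case against.** The strongest reply is that nothing may go wrong in practice. The CRF may well be graded. SAP 6.6.1 writes of causality being equal to named values and, in the same paragraph, defines discontinuation events by named values of the action-taken field. Both read like database values. That is a fair inference but not proof, and against it Protocol 10.1 names the CRF explicitly. Even with a binary field, a programmer would most likely code 'yes' as related, and the phrase in Protocol 11.5 about summarising all related events would naturally take such events in. This stands as an argument about likely consequence, and it is why the point is minor. It does not remove the contradiction in the text.

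A reader might infer three stronger things that the documents do not support.

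- **That the related-AE rate will be understated by a given number of percentage points.** Any such figure is an assumed count of affected subjects divided by the arm size. The documents give no AE counts, and Protocol 11.5 bases percentages on the Tolerability set, whose size is not known in advance.
- **That the SAP departs from the Protocol without declaring it in SAP 1.1.** On relatedness, SAP 6.6.1 follows Protocol 11.5, so there is no change from that section to declare. The conflict lies inside the Protocol, between 10.1 and 11.5, and the SAP inherits it.
- **That the SAP's rule for partial dates is a second conflict of the same kind**, because Protocol 11.5 says that no missing-data handling applies to the other variables. That statement cannot be an absolute ban: Protocol 11.5 itself applies a rule for missing relationship, and Protocol 11.1 expects data handling conventions and leaves further detail to the SAP.

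**Conclusion.** The point holds as a minor internal inconsistency: the rule is wrong as written for the field that Protocol 10.1 describes. Its effect takes one of three forms.

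- **Graded CRF:** no effect on any result; the wording of 10.1 is wrong.
- **Binary CRF, with 'yes' sensibly coded as related:** no event is lost from the outputs, but the coding would not be the one that the plan specifies.
- **Binary CRF, with the SAP rule applied literally:** every event marked 'yes' is left out of the three related-AE outputs, and only events with missing relationship remain.

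The third is the least likely, and its size cannot be given without AE counts. Confidence is high that the texts conflict. It does not extend to any effect on results, which rests on a CRF that is not among the documents. Neither the primary LDL conclusion nor the overall AE picture is in question.

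**What to change.** Before database lock, look at the relationship field in the CRF.

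- **If it is binary:** state in Protocol 11.5 and SAP 6.6.1 that an AE is product-related when relationship is 'yes' or missing, and remove the four graded terms. A two-value field cannot recover gradations such as possible or unassessable, so the report should describe related events as those marked 'yes' or left blank.
- **If it is graded:** replace the no/yes entry in Protocol 10.1 with the scale actually used, and keep the rule in Protocol 11.5 and SAP 6.6.1 as it is.

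The cost is one sentence in each of two places, or one line in one place. No new data, visits or analyses are needed. A Protocol edit goes to the Ethics Committee under Protocol 14.1. In the binary case, Protocol 11.8 also allows a departure from the Protocol's statistical plan to be documented and justified in the SAP, so the SAP sentence with an entry in SAP 1.1 could be in place before lock while the Protocol text is brought into line.

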## Menarini Group

Sponsor: A. Menarini Industrie Farmaceutiche Riunite S.r.l.

Amended Protocol Version 4.0 of 16.04.2018

Study Code: MEIF/16/MOF-Col/001

### Laboratory parameters

Summary statistics of raw data and change from baseline at each assessment time point for each laboratory parameter will be presented overall and by treatment group.

Laboratory test results will be classified by the low/normal/high classification based on local laboratory normal ranges. A frequency table for low/normal/high classification will be presented overall and by treatment group for each laboratory parameter. A listing of all out of range laboratory parameters will be provided with values flagged to show the classification relative to the laboratory normal ranges.

Vital signs, weight, waist circumference, Index of Central Obesity (ICO), Body Mass Index (BMI), Hepatic Steatosis Index (HSI), Lipid Accumulation Product (LAP).

Heart rate and blood pressure will be measured in orthostatic and clinostatic position. Summary statistics of raw data and change from baseline at each assessment time point for each parameter will be presented overall and by treatment group.

### Deaths

All deaths occurred will be listed together with all their details.

### Pregnancy test results

Any pregnancies reported will be listed.

### **11.6 Subgroup analysis**

No subgroup analyses are currently planned.

### **11.7 Protocol violations and blind review**

Protocol deviations will be detected throughout the study and reported by means of a specific form. All cases of prospectively defined protocol deviations (PD) will be identified prior to clinical database lock/unblinding and included in the clinical database. Certain deviations may stipulate that data collected from the patients will be excluded from analysis population(s). All exceptional cases and the final decisions on the allocation of patients to populations will be fully defined, documented and approved by the Sponsor study team during the blind review meeting, which will be held before data base lock and before breaking the blind.

